# 8. RANDOMIZATION AND BLINDING

The subjects will be randomized into the study and stratified by site. If a subject meets the eligibility criteria, he/she will be equally allocated (with a 1:1 ratio) to one of the two (2) treatment groups, based on a stratified randomization scheme random number generator.

#### 9. ADMINISTRATION OF TREATMENT

The treatment administrator will determine all motor thresholds (MTs) and administer the treatments. An independent rater will evaluate the patient following treatment and complete the subject assessment scales. The principle investigator, treatment administrator, independent rater and study subjects will all be blinded to the treatment being administered. At the beginning of the trial individual MTs will be measured by placing the assigned coil above the hand area of the motor cortex. All studied groups will receive stimulations over the prefrontal cortex, 6 cm anterior to the 'hot spot' (i.e., the left dorsolateral prefrontal cortex) for stimulation of the abductor policies brevis in the hand area. Each DTMS treatment (for active and sham groups) will be conducted as follows: Before starting each treatment, treatment administrators and subjects will be instructed to insert earplugs to lessen any possible adverse effect on hearing. Then, the MT will be measured by delivering single stimulations to the motor cortex. The MT is measured by gradually increasing the intensity. This is done by using the single pulse mode and applying one pulse every 5 sec, i.e. 0.2 Hertz. The electrical activity in abductor pollicis brevis is then recorded using surface electrodes. Threshold is defined as the lowest intensity of stimulation producing motor evoked potentials of at least  $50\mu V$  in 5 of 10 trials. After defining the motor threshold, the coil will be positioned anterior to the hot spot (i.e., the left dorsolateral prefrontal cortex) using the ruler on the subject's cap, and an rTMS session will be performed at 120% of the motor threshold. At the beginning of each treatment session the operator will apply one short trial train of 0.5 sec, 10 Hz, at a power output of 120% of the MT to test whether the subject responds well to the train. The operator will ask the subject if the treatment is tolerable. In case of excessive motor activation, the coil will be moved up to 1 cm forward, and the operator will re-evaluate whether the problem has been resolved. In case the problem has not been resolved, the operator may tilt the coil along the right-left axis, and again re-evaluate whether the problem has been resolved.

In case the subject has difficulty sustaining the trial train, the operator will apply trial trains gradually, in order to help the subject become accustomed to the treatment [the detailed scheme is specified in the Instructions for Use]. At the baseline (first) treatment the subject should receive a treatment at a power output of 100% of the measured motor threshold. At treatment #2 the subject should receive a treatment at a power output of 110% of the measured motor threshold. At treatment threshold. At treatment #3 and on the subject should receive

a treatment at a power output of 120% of the measured motor threshold. This is in order to help the subject become accustomed to the treatment.

The MT of each subject will be determined once a week. In case the MT found is higher or lower than the value found at the baseline by more than 5%, the operator should redetermine the MT. In case the MT is still higher than the value found at the baseline by more than 10%, then the treatment intensity should be set based on 110% (and not higher) of the MT found at the baseline. For example, if the MT found at baseline was 60% of the stimulator power output, then the maximal value of MT used for computation of treatment intensity can be no more than 66% of the stimulator power output (i.e. treatment will be applied at no more than 66 X 1.2 of the stimulator power output). In case the MT is lower than the value found at the baseline by more than 5%, then the principal investigator should approve the MT value, and the treatment intensity should be set based on the MT value found.

The treatment group will receive the following dose of DTMS treatment: 10 Hz, 120% MT, 3 sec pulse train, 15 second intertrain interval, 60 trains, total of 1800 pulses per session with duration of about 18 minutes per session each day. The control group will receive inactive/sham treatment with identical parameters. Study subjects will be asked a forced choice question whether they think they received a real or a sham treatment and the reason for their response, at the end of the first treatment session. Subjects will be told that face and hand twitching may occur due to either sham or active treatment and they will be instructed to sit with their arms crossed and folded.

During the treatment procedure, the treatment administrator will observe the subject closely for any sign of imminent seizure activity or muscle twitching. Presence of a physician or nurse trained in seizure management, emergency equipment (oxygen, suction, blood pressure monitor, and CPR equipment) and antiepileptic medications will be readily available in the immediate vicinity. Subjects will be informed of the risk of permanent hearing loss if an earplug should become detached or fall out. Subjects will be asked to immediately report any loosening or detachment of an earplug during DTMS and treatment will be stopped if a subject reports or if an investigator observes that an earplug has loosened or has fallen out. In the case of coil overheating a warning is displayed and the treatment administrator is instructed to remove the coil from the subject. The coil will cool down within several minutes and then treatment is resumed. Any events of coil overheating, removal and treatment resumption will be recorded.

Subject participating in the study will not be allowed to meet with each other before, during and after assessment or treatments in order to maintain study blinding.

# **10. CONCOMITANT THERAPY**

The following medications will not be allowed throughout the study: antidepressants, stimulants, and antipsychotics indicated for psychotic episode.

The following medication will be allowed throughout the study: Insomnia medications prescribed prior to commencement of treatment may be continued during the study (up to 3mg Lorivan, or equivalent).

Only the following insomnia medications (one or more) may be prescribed during the course of the study:

- Zolipidem (p.r.n. up to 10 mg/day orally or Zolipidem CR (6.25 or 12.5 mg/day orally).
- Zaleplon ( p.r.n. up to 20 mg/day orally)
- Zopiclone ( p.r.n up to 15 mg/day orally or eszopiclone ( p.r.. up to 3 mg/day orally)
- Benzodiazepines up to a dose equivalent to 3.0 mg of Lorazepam or equivalent

Acetaminophen or other medications for treatment of local pain, dental pain or headaches will be allowed, as necessary.

Medications for general medical conditions will be allowed. All medications taken by a subject (prescription or nonprescription) must be documented in the concomitant therapy section of the CRF. This includes medications taken within 30 days before treatment initiation and during the course of the study.

For any medication given as a treatment for a new or worsening condition, the condition must be documented on the Adverse Event Form of the CRF.

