# 7.3. Subject Exclusion Criteria:

- Currently on Nicotine Replacement Therapy (NRT) or smoking cessation drugs (e.g., Zyban, Chantix, etc.) or undergoing behavioral smoking cessation interventions.
- Cognitive or functional disability, diagnosed according to DSM-5 criteria.
- Active psychiatric disorder according to DSM-5 (Axis I and Axis II) criteria within the last year.
- Current alcohol or other substance abuse or dependence.
- Alcohol or other substance abuse or dependence during the last 12 months before recruitment.
- Subject is smoking any other form of tobacco or other substances.
- Subject is taking psychotropic medications on a regular basis.
- Subjects with a high risk for severe violence or suicidality as assessed during the screening interview.
- Subjects who suffer from an unstable physical disease such as high blood pressure (>150 mmHg systolic / diastolic > 110 mmHg) or acute, unstable cardiac disease.
- History of epilepsy or seizure (EXCEPT those therapeutically induced by ECT).
- Increased risk of seizure for any reason, including prior diagnosis of increased intracranial pressure (such as after large infarctions or trauma), or history of significant head injury or trauma with loss of consciousness for ≥ 5 minutes.
- History of any metal in the head (outside the mouth).
- Metallic particles in the eye, implanted cardiac pacemaker or any intracardiac lines, implanted neurostimulators, intracranial implant (e.g., aneurysm clips, shunts, stimulators, cochlear implants, or electrodes) or implanted medical pumps.

- Individuals with a significant neurological disorder or insult including, but not limited to:
  - Any condition likely to be associated with increased intracranial pressure
  - Space occupying brain lesion
  - History of cerebrovascular accident
  - Transient ischemic attack within two years
  - Cerebral aneurysm
  - Dementia
  - Mini Mental State Exam score of less than or equal to 24
  - Parkinson's disease
  - Huntington's chorea
  - Multiple sclerosis
- Subjects suffering from frequent and severe migraine headaches.
- Subjects suffering from significant hearing loss.
- Subjects taking pro-convulsant medications (e.g., antidepressants or antipsychotic medications).
- Previous treatment with TMS.
- Subjects who cannot communicate reliably with the investigator or who are not likely to cope with the requirements of the experiment.

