## 11.1.4. Treatment Phase

During the treatment phase subjects will receive daily prefrontal DTMS, 5 days per week for 3 consecutive weeks, followed by one weekly session for three weeks (for a total of 18 treatments over 6 weeks). Subjects will be asked to select a target quit date (TQD). The TQD will be scheduled within 7-14 days of the first treatment session, to allow for a minimum of 7 days of treatment before the quit attempt. Subjects will be instructed not to try to quit smoking prior to their TQD.

Subjects will be asked to refrain from smoking for two hours prior to the baseline visit and prior to all the treatment sessions. Prior to treatment stimulation onset, a smoking related cue/provocation will be presented to the subject. The smoking cue/provocation will consist of holding and handling a cigarette from the brand of cigarettes the subject is accustomed to smoke and viewing smoking related pictures for a period of 5 minutes. Immediately after the offset of the smoking cue/provocation presentation (while memory is reactivated) active or sham DTMS stimulation will be administered.

During the treatment phase, assessment visits will be performed weekly at weeks 2, 3, 4, 5 and 6 weeks from start of treatment. Assessment visits will be performed prior to the treatment session. Participants will be asked to keep a record of their smoking behavior on a diary card. At each of the weekly visits, smoking behavior will be evaluated, diary cards reviewed, information collected on changes in concomitant medications and adverse events, and urine cotinine levels monitored. Nicotine craving and nicotine dependence/withdrawal questionnaires will also be administered at each of the weekly visits. Subjects will be provided with a self-help educational booklet on smoking cessation ("Clearing the Air: How to Quit Smoking...and Quit for Keeps" National Cancer Institute 95-1647) and up to 10 minutes of brief counseling regarding smoking cessation will be provided at the end of each weekly visit in accordance with AHRQ Guidelines.

All procedures to be performed during the different visits are listed in the Time and Events Schedule in Attachment 1.

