# 12.2. Withdrawal from the study

A subject will be withdrawn from the study for any of the following reasons:

- Lost to follow up
- Withdrawal of consent
- Subject is not compliant with requirements of the study, including inclusion criteria and exclusion criteria
- The study is prematurely stopped or halted (e.g. clinical halt)
- The investigator believes that for safety reasons (e.g. an adverse event) it is in the best interest of the subject to stop treatment
- Subject's motor threshold cannot be located.
- Subject becomes pregnant.
- Subject has significant tremor in any limb.
- Subject experiences a seizure.
- Subject misses > 4 treatments during the daily treatment phase or > 3 consecutive treatments.

When a subject withdraws before completing the study, the reason for withdrawal will be documented on the CRF.

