### 15.2. Procedures

#### 15.2.1. All Adverse Events

All adverse events will be reported from the time a signed and dated informed consent form is obtained until completion of the last study-related procedure. Events meeting the definition of serious adverse events must be reported using the Serious Adverse Event Form, including serious adverse events spontaneously reported to the investigator within 30 days after the subject has completed the study (including post study follow up).

All events that meet the definition of a serious adverse event will be reported as serious adverse events, regardless of whether they are protocol-specific assessments. All adverse events, regardless of seriousness, severity, or presumed relationship to study treatment must be recorded using medical terminology in the source document and the CRF. Whenever possible, diagnoses should be given when signs and symptoms are due to a common etiology (e.g., cough, runny nose, sneezing, sore throat, and head congestion should be reported as "Upper respiratory infection"). Investigators must record in the CRF their opinion concerning the relationship of the adverse event to study treatment. All measures required for adverse event management must be recorded in the source document and reported according to sponsor instructions. In the case of a seizure, the investigators will provide to those patients experiencing a seizure a letter documenting that the seizure was experimentally produced. Other potential adverse events which could occur include psychiatric complications (e.g., mania, changes in behavior, hostility, agitation, depression and suicidality), headache, neck pain, intensification of existing headaches, tinnitus, and temporary or permanent hearing loss. The study personnel staff will be responsible for observing the study subjects during the weekly assessments and follow-up visits for such adverse events. In the case of an adverse event, the study investigator will prescribe the appropriate treatment and if appropriate, the subject will be terminated from the study to ensure subject safety.

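### Section 10's on-study drug rules do not carry forward the pro-convulsant exclusion of section 7.3, so it is unclear whether stimulation must stop when such a drug is started

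*Protocol*

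**What the plan says.** At entry, protocol section 7.3 excludes "Subjects taking pro-convulsant medications (e.g., antidepressants or antipsychotic medications"). The criterion covers the whole pro-convulsant class. Antidepressants and antipsychotics are examples, and neither is qualified by the reason for use. A separate criterion in the same list excludes raised seizure risk from any cause.

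Once the subject is in the study, section 10 lists what is prohibited: "The following medications will not be allowed throughout the study: antidepressants, stimulants, and antipsychotics indicated for psychotic episode". The same section then gives two open allowances: "Acetaminophen or other medications for treatment of local pain, dental pain or headaches will be allowed, as necessary", and "Medications for general medical conditions will be allowed". Neither mentions pro-convulsant drugs or refers back to section 7.3.

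Two other sections bear on the point. Section 12.2 lists among its grounds for withdrawal: "Subject is not compliant with requirements of the study, including inclusion criteria and exclusion criteria". Section 15.2.1 names possible adverse events including "psychiatric complications (e.g., mania, changes in behavior, hostility, agitation, depression and suicidality"), and says that when an adverse event occurs "the study investigator will prescribe the appropriate treatment and if appropriate, the subject will be terminated from the study to ensure subject safety".

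**The concern.** The entry criterion shows that the sponsor regards a pro-convulsant drug as incompatible with this stimulation. That judgement should apply for as long as stimulation is given, because the hazard comes from having the drug and the stimulation together and not from when the drug was first taken. Section 10 is where a site will look when a subject needs a new medicine, and its rule differs from the one in section 7.3. If a site follows section 10 alone, a subject could be stimulated while taking a drug that would have kept that subject out of the trial. If it follows section 12.2, the subject may be withdrawn for a drug that section 10 allows. Sites could reasonably act differently, and what is at stake is seizure risk.

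**Working it through.** No figure in the plan is in question, so the check sets the sections side by side.

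**Step 1: entry rule against on-study rule, by type of drug.**

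| Drug | Section 7.3 (entry) | Section 10 (on study) |
|---|---|---|
| Antidepressant | Excluded, named example | Barred |
| Stimulant | Not named | Barred |
| Antipsychotic for a psychotic episode | Excluded, named example | Barred |
| Antipsychotic for another reason | Excluded, named example | Not clearly barred |
| Any other pro-convulsant drug, used for pain or headache | Excluded as a class | Allowed |
| Any other pro-convulsant drug, used for a general medical condition | Excluded as a class | Allowed |

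The two rules agree on antidepressants, and section 10 is explicit about stimulants where section 7.3 is not. They part in the last three rows.

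**Step 2: can the gap be reached?** Section 15.2.1 foresees mania, hostility and agitation, tells the investigator to treat, and makes termination conditional. An antipsychotic given for agitation is not, on the face of it, given for a psychotic episode. Headache is also on the section 15.2.1 list, and section 2.4 calls it an expected effect in the preliminary study, so the pain and headache allowance is likely to be used. The protocol does not say whether any drug used under it is pro-convulsant, and section 10 does not ask the site to check.

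**Step 3: does section 12.2 settle it?** There are two readings.

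- *The exclusion criteria continue to apply during the study.* A subject who starts a pro-convulsant drug then meets an exclusion criterion and is withdrawn. But section 10 says that drugs in the allowed classes may be taken, so the two sections conflict.
- *The clause concerns subjects found not to have been eligible at entry.* Section 12.2 then says nothing about a newly started drug, and the gap stays open. Some support for this reading is that section 12.2 lists new pregnancy and an on-study seizure separately, although pregnancy and a history of seizure are already exclusion criteria. The separate entries would not be needed if the general clause plainly covered criteria met after entry.

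The text does not decide between the readings, and either one leaves something to correct.

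**Step 4: do other safeguards settle it?** Section 11.1.4 provides a weekly check: "At each of the weekly visits, smoking behavior will be evaluated, diary cards reviewed, information collected on changes in concomitant medications and adverse events". Section 10 requires every drug to be recorded, and the condition behind any new treatment to go on the Adverse Event Form. Section 11.4.5 assesses adverse events at each visit. Section 9 requires seizure-trained staff and equipment nearby. These measures detect a new drug or respond to a seizure. None says which drugs are incompatible with continued stimulation. The remaining route in section 12.2, stopping when the investigator believes it is in the subject's interest, depends on individual judgement.

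**The case against.** A reader might infer that the protocol permits a drug that bars entry to be started during the stimulation course. The documents do not support that, for four reasons.

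- Section 12.2 is mandatory in form and refers to the exclusion criteria. Together with the section 7.3 criterion on raised seizure risk, it can be read as a limit on the broad classes allowed in section 10. It also requires withdrawal once the investigator judges that stopping is safer.
- The antipsychotic wording in section 10 is ambiguous. It may describe the drugs themselves, meaning those whose indication is psychosis, and not the purpose of a particular prescription. On that reading such drugs are barred whatever the use.
- Antidepressants, one of the two examples in section 7.3, are barred outright on study, and so are stimulants. The gap is limited to antipsychotics for other indications and to pro-convulsant drugs that are not named.
- No pain, headache or general medical drug is identified as pro-convulsant anywhere in the protocol. How often the allowance would admit one cannot be judged from the document.

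The antipsychotic route also needs an unusual sequence: a new psychiatric complication, treated with an antipsychotic, in a subject whom the investigator keeps on stimulation.

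All of this stands, and it keeps the point minor. It does not remove the inconsistency. The first argument works only by setting section 12.2 against an express allowance in section 10, and the second shows that section 10 can be read in two ways. A rule meant to prevent seizures should not depend on which reading a site adopts.

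**Conclusion.** The concern holds as an inconsistency. Section 7.3 treats pro-convulsant drugs as disqualifying. Section 10 does not carry that forward, and section 12.2 either conflicts with section 10 or does not reach the case. The protocol therefore leaves unclear whether stimulation must stop when such a drug is started. It does not amount to a demonstrated permission to stimulate subjects on these drugs.

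The size is minor. The number of subjects affected is unknown, because the protocol gives no rate of new medication use and names no pro-convulsant drug in the allowed classes. The hazard concerns the active arm, since sham treatment is described as inactive. Because sites are blinded, any rule has to apply to both arms. Sample size, power and alpha are not affected. The conclusion assumes that the reason for the entry exclusion, seizure risk under stimulation, applies equally to a drug started after entry.

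**What to change.** Add one sentence to section 10: *During the treatment phase, all medications allowed in this section remain subject to the pro-convulsant exclusion of section 7.3 (including any antipsychotic, whatever the indication); if such a drug is started, stimulation stops.*

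The limit to the treatment phase is deliberate. Section 10's present prohibition runs for the whole study. Simply deleting the qualifier on antipsychotics would extend an unqualified ban to the 4 month visit, long after the last stimulation in week 6, when the reason for it no longer applies.

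The cost is a wording change and a note to sites, with no new procedure. It may lead to a few treatment stops. A subject who drops out as a result is classified as non-abstinent under section 13.9.8. The protocol gives no basis for estimating how many that would be.

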# **11. STUDY EVALUATIONS**

# **11.1. Study Procedures**

## 11.1.1. Overview

The Time and Events Schedule provided in Attachment 1 summarizes the frequency and timing of treatment and assessments. The trial will consist of 3 phases:

- 1. Pre-study Screening phase;
- 2. Baseline Phase;
- 3. Treatment phase (6 weeks); and
- 4. Follow-up phase (4 months).

Efficacy measures to be used in the study include:

- Self-reporting (nicotine inventory) of cigarette consumption
- Biochemical Verification using urine cotinine levels (nicotine metabolite)
- Nicotine Craving Scale (7 point VAS scale)
- Self-administered Fagerstrom Test of Nicotine Dependence (FTND)
- Minnesota Nicotine Withdrawal scale (MNWS)
- Self-administered Tobacco Craving Questionnaire (TCQ-SF)

Safety evaluations will include adverse event monitoring, vital signs, physical examination, auditory threshold testing, MMSE and BSRT cognitive tests.

